7.1.1.1 Hepatic Dose-Limiting Toxicity

Any one of the following study drug-related events will be considered a hepatic DLT:

7.1.1.2 Hematologic Dose-Limiting Toxicity

Any of the following events will be considered a DLT:

7.1.1.3 Dermatologic Dose-Limiting Toxicity

Any of the following events will be considered a DLT:

Protocol Amendment No.: 07

Other Dose-Limiting Toxicities 7.1.1.4

Any of the following events will be considered a DLT:

Management Algorithms for Immuno-Oncology Agents 7.1.2

Immuno-oncology agents are associated with irAEs that can differ in severity and duration from AEs caused by other therapeutic classes. BMS-986258 and nivolumab are considered I-O agents

Protocol Amendment No.: 07

in this protocol. Early recognition and management of irAEs associated with I-O agents may mitigate severe toxicity. Management algorithms have been developed from extensive experience with nivolumab to assist investigators in assessing and managing the following groups of irAEs:

- Gastrointestinal
- Renal
- Pulmonary
- Hepatic
- Endocrinopathies
- Skin
- Neurological
- Myocarditis

The clinical nature of AEs noted with BMS-986258 will determine the role of the algorithms for use in toxicities related to its use in this study. The algorithms recommended for the management of irAEs in this protocol are in Appendix 8.

7.2 Method of Treatment Assignment

During the screening visit, the investigative site will call into the enrollment option of the IRT designated by BMS for assignment of a 5-digit participant number that will be unique across all sites. Enrolled participants, including those not dosed, will be assigned sequential participant numbers starting with ________. The patient identification number (PID) will ultimately be comprised of the site number and participant number. For example, the first participant screened (ie, enrolled) at site number will have a PID of ________. Once it is determined that the participant meets the eligibility criteria following the screening visit, the investigative site will call the IRT to assign the participant into the open dose panel.

Participants will not be replaced if they are discontinued from the study secondary to an AE unless the AE can be determined to be unrelated to treatment.

During dose escalation, all participants will be assigned to Part A until the decision is made to escalate to the third dose cohort. Subsequently, treatment in Part B will be initiated, and dose escalation in the 2 parts will occur in parallel. In addition, Part A1 can be initiated independently, using all available safety and PK data and may be run in parallel with Parts A and B. Treatment assignments for participants eligible for Part A, Part A1, and Part B will alternate between the 3 parts, with consecutively treated participants assigned to different parts through IRT whenever possible and according to the corresponding inclusion criteria. If there are no openings available in the part to which the subject would be assigned by this algorithm, then the subject will be assigned to the next open part/cohort.

In addition, participants enrolled in monotherapy or combination PD cohorts will be assigned to dose levels that are already established as safe based on data coming from the corresponding dose

Protocol Amendment No.: 07

escalation cohort. The participants assigned in Part A and B NSCLC PD cohorts will need to pass eligibility for selection based on Criteria Section 6.1).

7.3 Blinding

This is an open-label, non-randomized study. The specific treatment to be taken by a participant will be assigned using an IRT. The site will contact the Interactive Response System prior to the start of study treatment administration for each participant. The site will record the treatment assignment on the applicable case report form (CRF).

[figure not shown]
7.4 Dosage Modification

Intra-participant dose escalation/reduction of BMS-986258 or nivolumab is not permitted in this study in order to allow better evaluation of the safety and efficacy at individual dose levels and schedules. No dose reductions of BMS-986258 or nivolumab will be allowed.

7.4.1 Dose Delays Due to Toxicity

Participants who experience the following must have all study drug(s) withheld:

• Potential DLTs, until DLT relatedness is defined.

- AE, laboratory abnormality, or concurrent illness that, in the judgment of the Investigator, warrants delaying study drug administration.
- Confirmed SARS-CoV-2 infection.

Criteria for participants who are required to permanently discontinue both study drugs are listed in Section 8.1. Participants not meeting guidelines for permanent discontinuation will be permitted to resume therapy based on the criteria specified below in Section 7.4.2. Participants eligible to resume study therapy will resume study therapy at the nominal treatment visit following their last received study medication dose.

The end of cycle tumor assessments, such as computed tomography (CT), magnetic resonance imaging (MRI), or positron emission tomography (PET), will continue on a Q8W schedule relative to the participant's first dose, regardless of any treatment delay incurred.

Protocol Amendment No.: 07

7.4.2 Criteria to Resume Treatment

Subsequent dosing with study therapy may resume once drug-related non-DLT AEs resolve to Grade 1 or baseline. Participants experiencing AEs not meeting criteria for permanent discontinuation as outlined in Section 8.1 may resume treatment with study medication under the following criteria:

Participants may resume treatment with study drug when the drug-related AE(s) resolve to Grade 1 or baseline value, with the following exceptions:

- Participants may resume treatment in the presence of Grade 2 fatigue
- Participants who have not experienced a Grade 3 drug-related skin AE may resume treatment in the presence of Grade 2 skin toxicity
- Participants with Grade 2 uveitis, episcleritis, iritis, eye pain, or blurred vision not meeting DLT criteria (Section 7.1.1.4) must resolve to baseline prior to resuming study therapy
- For participants with Grade 2 AST, ALT, or total bilirubin elevations, dosing may resume when laboratory values return to baseline, and management with corticosteroids, if needed, is complete
- Participants with combined Grade 2 AST/ALT and total bilirubin values meeting DLT criteria (Section 7.1.1.1) should have treatment permanently discontinued
- Participants with confirmed SARS-CoV-2 infection may resume treatment after 1) at least 10 days (20 days for severe/critical illness) have passed since symptoms first appeared or positive RT-PCR viral antigen test result, 2) resolution of acute symptoms (including at least 24 hours has passed since last fever without fever reducing medications), 3) evaluation by the Investigator with confirmation that there are no sequelae that would place the participant at a higher risk of receiving investigational treatment, and 4) consultation by the Medical Monitor. For suspected cases, treatment may also resume if SARS-CoV-2 infection is ruled-out and other criteria to resume treatment are met.

Prior to re-initiating on-study treatment in a participant with a dosing delay lasting 8 weeks due to SARS-CoV-2 infection, the Medical Monitor/designee must be consulted.

7.4.3 Management of Drug-related Infusion Reactions

For Grade 3 or 4 symptoms (severe reaction, Grade 3: prolonged [eg, not rapidly responsive to symptomatic medication and/or brief interruption of infusion]; recurrence of symptoms following initial improvement; hospitalization indicated for other clinical sequelae [eg, renal impairment, pulmonary infiltrates]; Grade 4: life-threatening; pressor or ventilatory support indicated):

• Immediately discontinue infusion of study drug. Begin an IV infusion of normal saline and treat the participant as follows: recommend bronchodilators, epinephrine 0.2 to 1 mg of a 1:1000 solution for SC administration or 0.1 to 0.25 mg of a 1:10,000 solution injected slowly for IV administration, and/or diphenhydramine 50 mg IV with methylprednisolone 100 mg IV (or equivalent), as needed. Participant should be monitored until the Investigator is comfortable that the symptoms will not recur. Study drug will be permanently discontinued except for a Grade 3 infusion reaction that returns to Grade 1 in less than 6 hours. Investigators should

Protocol Amendment No.: 07

follow their institutional guidelines for the treatment of anaphylaxis. Remain at bedside and monitor participant until recovery of the symptoms.

• In case of late-occurring hypersensitivity symptoms (eg, appearance of a localized or generalized pruritus within 1 week after treatment), symptomatic treatment may be given (eg, oral antihistamine or corticosteroids).

7.5 Preparation/Handling/Storage/Accountability

The IP should be stored in a secure area according to local regulations. It is the responsibility of the Investigator to ensure that IP is only dispensed to study participants. The IP must be dispensed only from official study sites by authorized personnel according to local regulations.

The product storage manager should ensure that the study treatment is stored in accordance with the environmental conditions (temperature, light, and humidity) as determined by BMS. If concerns regarding the quality or appearance of the study treatment arise, the study treatment should not be dispensed and BMS should be contacted immediately.

Study treatment not supplied by BMS will be stored in accordance with the package insert.

Investigational product documentation (whether supplied by BMS or not) must be maintained that includes all processes required to ensure drug is accurately administered. This includes documentation of drug storage, administration, and, as applicable, storage temperatures, reconstitution, and use of required processes (eg, required diluents, administration sets).

For study drugs not provided by BMS and obtained commercially by the site, storage should be in accordance with the product label.

Please refer to the current version of the IBs and/or Pharmacy Manual for complete preparation, storage, and handling information.

• Further guidance and information for final disposition of unused study treatment are provided in Appendix 2 and the Pharmacy Manual.

7.5.1 Retained Samples for Bioavailability/Bioequivalence/Biocomparability

Not applicable.

7.6 Treatment Compliance

Not applicable.

7.7 Concomitant Therapy

7.7.1 Prohibited and/or Restricted Treatments

The following medications are prohibited during the study (unless utilized to treat a drug-related AE):

• Immunosuppressive agents

Protocol Amendment No.: 07

• Immunosuppressive doses of systemic corticosteroids (except as stated in Section 6.2 and Section 7.7.2)

- Any concurrent anti-neoplastic therapy (eg, chemotherapy, hormonal therapy, immunotherapy, extensive, non-palliative radiation therapy)
- Any botanical preparation (eg, herbal supplements or traditional Chinese medicines) intended to treat the disease under study or provide supportive care. Use of marijuana and its derivatives for treatment of symptoms related to cancer or cancer treatment are permitted if obtained by medical prescription or if its use (even without a medical prescription) has been legalized locally.
- Administration of investigational SARS-CoV-2 vaccines is not allowed during the study. Participants may receive authorized or approved SARS-CoV-2 vaccines while continuing on study treatment at the discretion of the investigator.
- Treatment of active SARS-CoV-2 infections or high-risk exposures, including use of investigational therapies, is allowed and should be discussed with the Medical Monitor.

No concomitant medications (prescription, over-the-counter, or herbal) are to be administered during study unless they are prescribed for treatment of specific clinical events. Any concomitant therapies must be recorded on the CRF.

7.7.2 Other Restrictions and Precautions

Participants with a condition requiring systemic treatment with either corticosteroids (> 10 mg daily prednisone equivalent) or other immunosuppressive medications within 14 days of randomization or treatment assignment are excluded. Inhaled or topical steroids, and adrenal replacement steroid doses \leq 10 mg daily prednisone equivalent, are permitted in the absence of active autoimmune disease.

For participants who need to undergo elective surgery (not tumor related) during the study, it is recommended to hold study drug(s) for at least 2 weeks before and 2 weeks after surgery, or until the subject recovers from the procedure, whichever is longer. Prior to resuming study drug treatment, surgically-related AEs should resolve to ≤ Grade 1 or baseline and participants must meet relevant eligibility criteria as determined by the BMS Medical Monitor in discussion with the Investigator. The BMS Medical Monitor must be consulted prior to re-initiating treatment in a subject with a dosing interruption lasting > 8 weeks after the last dose.

7.7.2.1 Vaccinations

Any vaccination containing attenuated or inactivated virus may be permitted if clinically indicated. However, this must be discussed and documented with the BMS Medical Monitor prior to administration and may require a study drug washout period prior to and after administration of the vaccine. Inactivated influenza vaccination will be permitted on study without restriction. Any vaccination containing live virus, including live SARS-CoV-2 vaccines, is prohibited.

Protocol Amendment No.: 07

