As noted in the nonclinical studies in Section 3.2.1.3, BMS-986258 repeatedly administered to cynomolgus monkeys did not induce infusion-related or anaphylactoid reactions. However, because of the as yet unknown potential of infusion reactions with the administration of BMS-986258 in humans, although the first 25 participants treated with BMS-986258 monotherapy in doses ranging from 8 to 1200 mg did not present with infusion-related reactions, all participants receiving the first 2 doses of BMS-986258 monotherapy or in combination with nivolumab will

be closely monitored until post infusion for potential infusion reactions that could occur after either first administration or from repeat dosing of a novel mAb. In addition, the administration of BMS-986258 as monotherapy or in combination with nivolumab will occur at sites with medical monitoring and capability to manage infusion reaction or anaphylaxis.

Frequent safety assessments will be utilized by the investigators and Sponsor to determine whether dose modification, additional safety measures, or termination of the study is required at any time. In addition, AEs and SAEs will be reviewed regularly by the Medical Monitor/Study Director and the Pharmacovigilance group to look for trends and potential safety signals. Treatment of AEs will follow Institutional guidelines and recommended management algorithms as listed in the nivolumab prescribing information³⁰ and nivolumab IB³¹ and provided as appendices to the protocol.

It is unknown if treatment with BMS-986258 or BMS-986258 in combination with nivolumab increases the risk for contracting symptomatic SARS-CoV-2 infection or increases the severity or duration of symptoms. This unknown risk must be considered when enrolling a subject.

No additional safety monitoring or routine screening tests for all participants will be implemented because of the SARS-CoV-2 pandemic. However, eligibility for this trial may be impacted in participants with a recent episode of SARS-CoV-2 infection (please refer to Section 6.2 Exclusion Criteria).

Non-live COVID-19 vaccination is considered a simple concomitant medication within the study. However, the efficacy and safety of non-live vaccines (including non-live COVID-19 vaccines) in participants receiving BMS-986258 or BMS-986258 in combination with nivolumab is unknown.

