 - (6) QT interval corrected for heart rate using Fridericia's formula (QTcF) prolongation > 480 msec, except for right bundle branch block
 - (7) History of myocarditis, regardless of etiology
- v) History of or with active interstitial lung disease
- vi) History of chronic hepatitis as evidenced by the following:
 - (1) Positive test for hepatitis B surface antigen
 - (2) Positive test for qualitative hepatitis C viral load by polymerase chain reaction (PCR)
 - (3) Participants with positive hepatitis C antibody and negative quantitative hepatitis C by PCR are eligible. History of resolved hepatitis A virus infection is not an exclusion criterion.
 - (4) Additional testing or substitute testing per institutional guidelines to rule out infection is permitted.
- vii) Evidence of active infection that requires systemic antibacterial, antiviral, or antifungal therapy ≤ 7 days prior to the first dose of study drug (except for viral infections that are presumed to be associated with the underlying tumor type required for study entry).
- viii) Human immunodeficiency virus (HIV) or known acquired immunodeficiency syndrome:

CA031002 Anti-TIM-3 mAb

(1) For Parts A, A1, and B, known history of testing positive for HIV or known acquired immunodeficiency syndrome constitutes an exclusion criterion.

Note: Testing for HIV must be performed at sites where mandated by local requirements.

- (2) For Part C, HIV infection does not constitute an exclusion criterion if the following conditions are satisfied:
 - (a) Subject is in use of an antiretroviral therapy regimen for > 4 weeks.
 - (b) HIV viral load is undetectable or below the lower limit of detection as per local testing standards.
 - (c) CD4+ T-cell counts >= 350 cells/mL, up to 4 weeks prior to enrollment.
 - (d) Subject has no history of AIDS-defining opportunistic infections.
- ix) Any major surgery within 4 weeks of the first dose of study drug. Participants must have recovered from the effects of major surgery or significant traumatic injury at least 14 days before the first dose of study drug.
- x) Receipt of non-oncology vaccines containing live virus for prevention of infectious diseases within 4 weeks prior to first dose of study drug.
 - (1) The use of inactivated seasonal influenza vaccines (eg, Fluzone®) will be permitted on study without restriction.
- xi) Receipt of packed red blood cells or platelet transfusion within 2 weeks of the first dose of study drug unless agreed by the Medical Monitor.

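### Section 7.7.2.1 opens an approval route for attenuated-virus vaccines and, in the same paragraph, bars all live-virus vaccines

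*Combined protocol and SAP*

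**What the plan says.** Section 7.7.2.1 (Vaccinations) is one paragraph of four sentences.

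- The first grants a conditional permission: "Any vaccination containing attenuated or inactivated virus may be permitted if clinically indicated".
- The second sets the condition: "However, this must be discussed and documented with the BMS Medical Monitor prior to administration and may require a study drug washout period", both before and after the vaccine.
- The third allows inactivated influenza vaccine without restriction.
- The fourth is a flat ban: "Any vaccination containing live virus, including live SARS-CoV-2 vaccines, is prohibited".

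Before treatment, exclusion criterion 3e(x) in Section 6.2 rules out participants with "Receipt of non-oncology vaccines containing live virus for prevention of infectious diseases within 4 weeks prior to first dose of study drug". Section 3.3.6 adds that, with study drug on board, "the efficacy and safety of non-live vaccines (including non-live COVID-19 vaccines") are unknown.

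**The concern.** The first sentence sets 'attenuated' against 'inactivated', so it appears to admit something that has not been inactivated. Nothing limits the word to non-live products, and the protocol gives no definition that separates an attenuated-virus vaccine from a live-virus one. A reader who takes the word in its usual sense finds a named class of vaccine given an approval route at the top of the paragraph and barred at the bottom.

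This is an operative safety instruction in an immuno-oncology study. Appendix 8 makes corticosteroids a primary treatment for immune-related events, so some participants may be immunosuppressed while on study. A site and the Medical Monitor could follow the first two sentences in good faith, document their agreement, and still break the fourth. Section 9 allows no waivers or exemptions, so the result would be a protocol deviation.

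**Working it through.** No arithmetic applies; the check is a reading of each sentence against each class of vaccine. The one outside input is the assumption that an attenuated-virus vaccine is ordinarily live.

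| Vaccine class | Sentences 1 and 2 | Sentence 3 | Sentence 4 | Result |
|---|---|---|---|---|
| Inactivated influenza | Medical Monitor route | Unrestricted | Silent | Permitted; sentence 3 is the specific rule |
| Other inactivated virus | Medical Monitor route | Silent | Silent | Permitted on condition |
| Live-attenuated virus | Medical Monitor route | Silent | Prohibited | Conflict |
| Live virus, not attenuated | Silent | Silent | Prohibited | Barred |
| No virus in the product | Silent | Silent | Silent | Not addressed |

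Only the third row gives two answers.

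Next, which answer is meant? Sentence 4 carries no exception. Criterion 3e(x) applies the same live-virus test before first dose and likewise makes no exception for attenuated products. It is an eligibility window of 4 weeks and does not itself say what 'attenuated' means on study, but it points the same way as the ban. Section 3.3.6 treats even non-live vaccines as an unknown with study drug, which fits poorly with an intended route for live ones. The slip is therefore most likely in sentence 1.

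Last, does the fix depend on the assumption? If 'attenuated' means live-attenuated, deleting it removes the conflict. If it was meant only as another word for inactivated, deleting it loses nothing. If the sponsor had in mind some attenuated but non-live product, the text does not say so. The alternative wording, an express statement that live-attenuated vaccines are prohibited, would keep that permission and close the gap. Some correction is useful on every reading.

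**The case against.** The best case for leaving the text alone has three parts.

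- The overlap depends on a meaning that the protocol never states. That is correct, and it is why the meaning is given here as an assumption.
- The first sentence only permits, while the last prohibits. Nobody is required to give an attenuated vaccine, so a site that obeys the ban complies with every section. That also stands, and it is the main reason the point ranks low. But the section states no order of precedence, and a reader has to notice the conflict before choosing the stricter rule.
- A site cannot act alone, because the Medical Monitor must be consulted first. This narrows the path to harm without closing it, since the Medical Monitor works from the same paragraph.

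A reader might also infer a second contradiction, with Section 7.7.1. That section states "Administration of investigational SARS-CoV-2 vaccines is not allowed during the study", then "Participants may receive authorized or approved SARS-CoV-2 vaccines while continuing on study treatment at the discretion of the investigator", with no live or non-live qualifier. Read in isolation it seems to admit an authorized live SARS-CoV-2 vaccine. The documents do not support calling this an error. Section 7.7.2.1 belongs to the same Section 7.7 and bars live SARS-CoV-2 vaccines by name, and Section 3.3.6 says "Non-live COVID-19 vaccination is considered a simple concomitant medication within the study". Read together, the sections exclude such a product, and the documents do not show that one was authorized. What remains is an optional cross-reference.

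Nor should a reader infer from the Amendment 07 table of key changes that Section 7.7.1 was updated without the matching bar. The section cell of that row ends in a semicolon, and the table uses semicolons to separate section names. A second section may have been lost from the text available here, so the row cannot show what the edit covered.

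**Conclusion.** The point holds for Section 7.7.2.1 only, as a narrow patient-safety clarification. On the ordinary meaning of 'attenuated', which is an assumption, the paragraph both conditionally permits and prohibits live-attenuated vaccines, and the ban is very probably the intended rule.

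The consequence cannot be sized: the documents give no figure for how often such a vaccine would be offered. The on-study rule covers up to 96 weeks of treatment (Section 5.1.3), but that is a duration and not a measure of harm. Other inactivated vaccines, inactivated influenza vaccine and products containing no virus are untouched. Endpoints, dose-limiting toxicity evaluation, sample size and analysis do not change. It is worth correcting when convenient and gives no reason to delay the study.

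**What to change.** In the first sentence of Section 7.7.2.1, delete the words 'attenuated or'. Alternatively, keep the sentence and add that live-attenuated vaccines are prohibited. Either brings the paragraph into line with its own closing ban and with criterion 3e(x).

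As an option, add 'non-live' or a cross-reference to Section 7.7.2.1 where Section 7.7.1 permits authorized or approved SARS-CoV-2 vaccines. This would help readers but corrects no error. Nothing here loosens the rule for inactivated vaccines.

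The cost is one short wording edit. Appendix 2 requires IRB/IEC approval of protocol changes, so it should travel with the next planned amendment and not prompt one of its own. Data collection and the planned analyses need no change.
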